Cover page

Official Project Title: Reducing Pesticide Exposures in Child Care Centers

NCT # 03319927

Document: Study Protocol

Document Date: 8/13/2025

Study Protocol

UCSF IRB Study Application Section 8.0

8.2 HYPOTHESIS: Describe the hypothesis or what the study hopes to prove (Help Text updated 9/13):

1. Child care center staff who attend the IPM workshop will have significantly increased knowledge of IPM and hazards of pesticide use compared to their pre-workshop knowledge and compared to the control center staff.
- 2.: Post-intervention, the IPM intervention child care centers will have (a) higher numbers of written IPM policies, (b) more IPM practices, (c) fewer pest problems, and (d) higher director self-efficacy for pest management compared to pre-intervention and compared to the control centers.
3. Post-intervention, the IPM intervention child care centers will have lower concentrations and loadings of pesticides in dust compared to pre-intervention and compared to the control centers.
4. Post-intervention, children's personal exposure to pesticides, as measured by silicone wristbands, will be lower compared to pre-intervention and compared to that of children in the control centers.

8.3 AIMS: List the specific aims:

1. To determine if a nurse-led IPM workshop improves child care center staff's IPM knowledge.
2. To determine if an IPM intervention in child care centers (a) increases the number of IPM policies, (b) increases IPM practices, (c) decreases pest problems (i.e., number of pests present, pest debris), and (d) increases director's self-efficacy.

3. To determine if an IPM intervention reduces pesticide contamination in the intervention child care centers compared to the control centers.
4. To determine if an IPM intervention reduces children's and teachers' exposure to pesticides in the intervention child care centers compared to the children in the control centers.

8.4 DESIGN: Briefly describe the study design (e.g., observational, interventional, randomized, placebo-controlled, blinded, cross-over, cross-sectional, longitudinal, pharmacokinetic, etc.):

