Overview. The study participants include 90 child care center directors, 270 child care center staff, and 450 parents (mothers, fathers or legal guardians) and their preschool-age children, 3-5 years of age. The participants will be involved in the following procedures: (a) child care center directors will be interviewed by the UCSF research staff, (b) child care center staff will attend an educational workshop and complete a knowledge survey before and after the workshop, (c) parents/guardians will be given surveys to complete on their own or by interview about their family and child demographics and pesticide use at home, (d) children will have their height, weight, and waist circumference measured twice along with measurement of individual exposures using silicone wristbands before and after the intervention, and (e) research staff will collect dust samples in each center and conduct observations of the child care center environment and children's physical activity before and after the intervention.

Staff Roles. The research assistants' (RA) and child care health consultants' (CCHC) activities include:

1. Attend a one-day training on the intervention and data collection protocols. (CCHC/RA). The RA will achieve 90% inter-rater reliability with the PI on 2 observation instruments (Health and Safety Checklist and IPM Checklist).
2. Recruit child care directors through the local Resource and Referral Agencies (CCHC/RA).
3. Obtain signed consent forms from the child care directors (CCHC).
4. Identify 5 children per center and contact families and obtain signed consent forms. (CCHC/RA)
5. Conduct child care director interviews pre- and post-intervention (CCHC).
6. Complete Health and Safety and IPM Checklists. (RA)
7. Write-up the summary of the Checklist with photographs and narrative. (RA)
8. Collect anthropometric measures of the children, including height, weight, and waist circumference on 5 children per center pre- and post-intervention. (CCHC/RA)
9. Collect dust samples in the center and wristband measures for 5 children per center over two days pre- and post-intervention. (RA and CCHC together)

10. Prepare and provide 2 workshops for child care staff. (CCHC)
11. Review Checklist summaries with the director and establish 3-5 goals of the intervention. (CCHC)
12. Assist the child care directors to develop written health and safety policies. (CCHC)
13. Conduct monthly on-site (x3) or off-site (x3) (email, mail, phone) consultation. (CCHC)

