year 3, parents/guardians of enrolled children will be issued two ***silicone wristbands*** each: a blue one which they will be asked to wear continuously for 5 days, both at home and at the center, including while bathing and sleeping, and a yellow one they will be asked to wear at the center only, for 5 days. During the 5 days, the children will wear both wristbands simultaneously, and the CCHC will be present to assist with sample collection. On day one, the nurse CCHC will measure participating children's height, weight, and waist circumference. On 2 days, CCHCs will assess children's activity level using the Observation System for Recording Activity in Preschools (OSRAP). Using the OSRAP, CCHC observers will record the intensity of children's physical activity (1=stationery to 5=fast), location of activity, context of activity (teacher directed, child initiated), and interactions (none, child peer, provider, other adult). For all of the enrolled children, the CCHC will also assure that children's yellow wristbands are removed and sealed in child-specific storage bags at the end of each sampling day, and that the correct wristband is placed on the correct child on the 5 in-center collection days. All of the enrolled children will wear a wristband in the child care center over 5 days for at least 30 total hours. At some point during their child's sampling period, at a time convenient for them, parents/ guardians will be asked to complete a questionnaire in English or Spanish regarding their child's demographic and health characteristics, diet and physical activity habits at home (e.g., organic vs. conventional diet, indoor vs. outdoor play), home pesticide use, and any other possible sources of pesticide exposure, including through parents'/ guardian's occupations, residence with farmworkers, or residence near agricultural fields. Parents/guardians will also be asked to provide their home address for geocoding. Questionnaire items will be modeled upon pesticide exposure questions asked in other CERCH studies, including Center for Health Assessment of Mothers and Children of Salinas (CHAMACOS) and the recent silicone wristband study noted in Preliminary Studies. Two child care teachers per center will wear silicone wristbands for five days or 30 hours to measure pesticide levels.

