Post-Intervention Phase. During this phase, a research assistant will re-assess the center using the same observational checklists described for the Baseline Assessment, and the CCHC will also repeat all other aspects of Baseline Assessment data collection, including a director interview, the self-efficacy survey, dust collection, silicone wristband collection (children and teachers) and its attendant data collection from families, and anthropometric measurements. At Post-Intervention, however, no new children will be enrolled to participate. The same families who participated at Baseline will be invited to participate again, provided their child still attends the center and intends to be present on the sampling days.

Follow-up Study. We will also conduct a one-year follow-up study on pesticide exposure for all of the intervention centers, including both dust analyses and assessment of pests and pesticide products .

Sampling Procedures. The silicone wristbands will be sent de-identified to [name] laboratory at Oregon State University and the child care center's dust samples will be sent to Southwest Research Institute (SwRI) located in San Antonio, TX for analysis of multiple pesticides. They will be analyzed within a year of data collection and we will store the amount of

wristband or dust that is left over for 5 years to use in possible future analyses of other environmental chemicals or health markers.

8.11 INSTRUMENTS: List all questionnaires, surveys, interview, or focus group guides that will be used for this study:

If the instruments are not complete or not available because they will be developed as part of this study, describe the basic content or include an outline and submit the final versions to the IRB with a modification for approval prior to use.

1. IPM and Physical Activity (PA) Knowledge Survey – pre and post-workshop
2. IPM and PA Policy Checklist
3. Director interview
4. IPM Checklist ([name] et al., 2012)
5. Director IPM Interview
6. Director and child care provider Self-Efficacy ([name] et al., 2003) – modified Bandura
7. Demographic Survey for child care providers - sex, age, ethnicity,
8. Demographic Survey for parents - sex, age, ethnicity, BMI, health
9. CHAMACOS parent interview -modified as self-completed survey with major life events, physical activity
10. Child Anthropometrics
11. Dust samples ([name] et al., 2012)
12. Child activity measure modified OSRAP (A [name] et al., 2014)

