Specific Aim 3: To determine if an IPM intervention reduces pesticide contamination in the intervention IPM child care centers compared to the PA control centers. (a) **Unit of Analysis:** Child care centers. (b) **Dependent Variable:** Pesticide concentrations in dust. (c) **Independent Variables: Group, Time, and Cohort.** Tobit regression models were conducted with an additional random intercept term for child care center to account for correlations within centers across timepoints (baseline, post-intervention). The concentrations and detection of the 15 pesticides measured in dust were analyzed separately using the STATA command 'tobit'.

Specific Aim 4: To determine if an IPM intervention reduces children's exposure to pesticides in the IPM intervention child care centers compared to the children in the PA control centers. (a) **Unit of Analysis:** Enrolled children with complete wristband data at baseline and post-intervention aggregated by child care center. (b) **Dependent Variable:** Pesticides measured in children's wristbands worn at the child care. (c) **Independent Variables: Group, Time, and Cohort.** Pesticide concentrations analyzed in the silicone wristbands. (c) **Independent Variables: Group, Time, and Cohort.** Tobit regression models were conducted with an

additional random intercept term for child care center to account for correlations within centers across timepoints (baseline, post-intervention). The concentrations and detection of the 13 pesticides measured in dust were analyzed separately.

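### SAP Aim 4 appears to aggregate wristband values by center before a tobit, without a stated aggregation or non-detect rule; it also drops incomplete pairs and leaves the teachers unanalysed

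*SAP*

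**What the plan says.** SAP, Specific Aim 4, defines the unit of analysis as "Enrolled children with complete wristband data at baseline and post-intervention aggregated by child care center" and the outcome as "Pesticides measured in children's wristbands worn at the child care". The model is a tobit for each pesticide, with Group, Time and Cohort as independent variables and an "additional random intercept term for child care center to account for correlations within centers across timepoints (baseline, post-intervention". There is no child term. The section closes with "The concentrations and detection of the 13 pesticides measured in dust were analyzed separately", although Aim 4 concerns wristbands and the dust analysis in Aim 3 covers 15 pesticides.

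The SAP does not say whether the aggregate is an arithmetic mean, a geometric mean or something else. It gives no detection limits, no rule for how a non-detect enters the aggregate, no rule for when a center value counts as censored, and no missing-data method.

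Protocol 8.3, aim 4, asks whether the intervention "reduces children's and teachers' exposure to pesticides in the intervention child care centers". Protocol 8.9 has two teachers per center wear wristbands at baseline and repeats this post-intervention. Under Post-Intervention Phase no new children are enrolled, and families are invited again "provided their child still attends the center and intends to be present on the sampling days".

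**The concern.** A tobit needs each observation to be either an exact value or a value known only to lie below a stated limit. A summary over several children, some detected and some not, is in general neither. The analyst has to choose a number for each non-detect, a type of mean and a censoring rule for the result, and each choice moves the estimate. Aim 4 is the only aim on personal exposure, so its effect estimate would rest on choices that cannot be recovered from the plan.

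Two further gaps bear on what Aim 4 can answer. Children with a baseline wristband but none post-intervention are removed entirely. One of the two groups named in the protocol's aim is not analysed.

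**Working it through.** **1. Reading of the unit.** The SAP says the data are aggregated by center, and its only random term links a center's two timepoints. Both fit one value per center and timepoint. Using a tobit and analysing detection implies that some wristbands are non-detects, although no rate is given.

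**2. Why the center value has no valid limit.** Take 5 children per center (Protocol 8.9, Staff Roles), m of them detected with values summing to S. The arithmetic mean then lies between S/5 and (S + (5 − m)·LOD)/5, an interval of width (5 − m)·LOD/5. With two non-detects the width is 0.4·LOD. The location of the interval differs by center. That is interval censoring with center-specific limits, not left censoring at the LOD. For a mean of logs the lower end is unbounded.

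**3. Size.** The documents give no power or effect calculation to reproduce. The head-counts agree: 90 × 5 = 450 children and 90 × 3 = 270 staff.

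Simulation model: log value = center + child + residual + δ·Group·Time, with δ = ln(0.5) = −0.693. The 50% is illustrative; Protocol 8.5 cites it as an upper figure for homes, not as a design assumption. Other assumptions:
- 84 to 90 centers in two equal groups, 5 children each (the documents give 90 planned and 85 for survey and observational data);
- 30 to 90% detected at baseline;
- log SDs (center/child/residual) of 0.5/0.3/0.5, 0.7/0.5/0.8 and 1.0/0.7/1.2;
- a center value treated as censored when at or below the LOD;
- 40 to 60 runs per cell.

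Median estimate divided by the truth:

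| Analysis | Arithmetic center mean | Mean of logs (middle SDs only) |
|---|---|---|
| Non-detect = LOD | 0.54–0.93 | 0.39–0.85 |
| Non-detect = LOD/√2 | 0.83–0.98 | 0.72–0.94 |
| Non-detect = LOD/2 | 0.96–1.16 | 0.92–1.01 |
| Non-detect = 0 | 1.02–1.35 | not defined |
| Child-level tobit (no aggregation) | 0.94–1.05 | |

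On the ratio scale, the lowest cell was −0.267, and exp(−0.267) = 0.77, so a 50% reduction would be reported as about 23%. The highest was 1.35 × (−0.693) = −0.936, and exp(−0.936) = 0.39, about 61%.

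With all three SDs at 0.8, LOD/√2 and 20/40/60% non-detects, a 300-run simulation gave −0.553/−0.442/−0.320 for the aggregated tobit. Divided by −0.693 that is 0.80/0.64/0.46. The child-level tobit gave −0.682/−0.694/−0.685, or 0.98/1.00/0.99. Other runs at the same SDs and LOD/√2 gave 0.84/0.69/0.59 for the mean of logs, and 0.85/0.67/0.46 when a center counted as censored only if all its children were non-detect. For LOD/2 they gave 0.92/0.80/0.70 (logs) and 1.02/0.97/0.94 (arithmetic).

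With a true ratio of 0.80 the pattern was similar but noisy. The child-level ratios themselves ran from 0.86 to 1.16, because a run SD of 0.21 over 40 runs is 0.21/√40 = 0.033, or 15% of |ln 0.8| = 0.223. With no true effect, medians stayed within about 0.02 of zero.

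**4. Complete pairs.** No dropout rate is stated. Losses of 10/20/30/40% of 450 would leave 405/360/315/270 pairs. An uncensored check had 22 to 27% leaving and truth −0.693. The complete-pair estimate was −0.700 if leaving is unrelated to exposure, −0.655 if it depends on the post-intervention value equally in both groups, −0.773 if only in the IPM group, and −0.592 if only in controls.

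**5. Teachers.** 2 × 90 = 180 planned (2 × 85 = 170). No teacher exposure analysis appears in the SAP.

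**The case against.** The strongest reply is that aggregation before the tobit is not certain. The SAP's opening paragraph presents the tobit as a method for repeated and clustered outcomes, and the unit of analysis begins with enrolled children. If the model was in fact fitted to children, the censoring problem disappears. That reading is possible but less natural, and it leaves the two wristbands of one child without a child term.

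A reader might infer that the Aim 4 effect is biased towards zero. The documents do not support that as a fact. The word used is aggregated, not averaged; no non-detect rule or detection rate is given; and the bias runs from strong attenuation through almost none to exaggeration. Any single attenuation percentage describes one assumed scenario. Nor did the simulations produce a spurious effect where none existed.

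Equal weighting of centers is a legitimate target for an intervention delivered to centers, so unequal numbers of children per center are not in themselves a fault.

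On teachers, one might say that half the aim is unanswered. That goes too far: protocol hypothesis 4 names only children, the design has five children to two teachers per center, and the SAP restates the aim for children alone. The mismatch with protocol aim 4 and with the data collected is still real and unexplained.

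One might also see a contradiction in wear time. Staff Roles item 9 speaks of "wristband measures for 5 children per center over two days pre- and post-intervention", while the Baseline Assessment text says "All of the enrolled children will wear a wristband in the child care center over 5 days for at least 30 total hours". Item 9 is in a list of staff tasks and may describe collection visits, so this calls for clarification only. The documents also do not say that hours worn were recorded or that limits exist for each band.

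**Conclusion.** The concern holds as a defect of method and specification. On the natural reading, the Aim 4 tobit is fitted to center values that have no valid censoring limit, under rules that are not stated. Under the assumed SDs and detection rates and a true 50% reduction:
- with non-detects at the LOD or LOD/√2 the estimate is typically attenuated, to between 0.39 and 0.98 of the true log effect, mostly 0.95 or lower;
- at LOD/2 it is near-unbiased to attenuated in most settings (0.70 to 1.16 overall);
- at zero it can be exaggerated, up to 1.35.

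The child-level censored model recovered 0.94 to 1.05, within simulation error of 1. Direction and size in this trial cannot be determined from the documents. The simulations ignore the county-level assignment, and the child-level comparator in the 0.94 to 1.05 runs carried only a center intercept.

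Restriction to complete pairs certainly loses baseline information. Any bias from it can go either way. The missing teacher analysis follows from the text alone and needs no assumption.

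**What to change.** In SAP Aim 4:
- Fit a child-level random-effects tobit on log concentration for each pesticide, with child nested in center, a Group x Time term, Cohort as now, and non-detects censored at the laboratory's detection limit. State those limits and the percentage detected by group and time.
- Use all available baseline and post-intervention wristbands, and keep complete pairs as a sensitivity analysis. Report how many children lack a post-intervention wristband in each group. Using all data recovers baseline information but does not remove bias if leaving depends on the unseen post-intervention value.
- Fit the same model to the teacher wristbands, or state that the teacher part of protocol aim 4 was dropped and why.
- Adjust for hours worn only if they were recorded.
- Change dust to wristbands in the closing sentence.

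In Protocol 8.9, clarify whether the two days in Staff Roles item 9 are staff visits or wear time.

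The cost is SAP and protocol wording and a re-run on wristbands already collected. The downside is a slightly more complex model.
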